Protocol. Subjects will be identified for potential recruitment through electronic medical record review; directly through OHSU’s neurology clinics and through IRB approved advertisements. Subjects will receive the first study phase medications from the research pharmacy at the end of the baseline testing. The subject will be called weekly to ask about side effects or problems with the protocol. They will also be asked about falls. These contacts will be captured in case report forms. If there are problems, the investigator will call the subject or the subject will be brought into clinic to evaluate the problem. At 3 weeks, the subjects will have a phone call from one of the neurologists for safety; adverse events will be captured. At 6 weeks, the subject will return to the clinic for repeat testing with the measures captured at baseline and also the subjects will have ANT and SAI testing. The subject will be tested “off” their PD medications.

[figure not shown]

Figure 1. Study design

The subjects will then enter the 6-week washout period. Although the subjects will be on no experimental medications, they will continue to be called weekly to inquire about side-effects,

problems and falls. This is partly done to keep the subject involved in the protocol, as well as to collect data about falls. At the conclusion of the 6 weeks, the subjects will return to the clinic for repeat testing and to have medications dispensed for the final 6-week phase of the protocol. The final 6-week phase will be conducted exactly as was the first six-week phase with repeat testing at the end of the 6 weeks.

Subjects. Subjects will be 30 years or older, of either gender and any racial or ethnic origin. Women who are capable of child bearing must employ birth control. Pregnant women are not eligible to participate. The subjects will have idiopathic Parkinson's disease as determined from history and exam and lack of history or physical findings that would suggest another diagnosis or a parkinsonism-plus syndrome. Subjects may be Hoehn and Yahr stages II to IV. Subjects must be able to stand unassisted for a minute and to walk continuously for 2 minutes without assistance or assistive devices. The subjects must have a Montreal Cognitive Assessment (MOCA) of 23 or above and be judged to be able to appreciate the purpose of the research, give informed consent to participate, be able to cooperate with the testing and be compliant with taking the experimental medications.

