Exclusion criteria include: significant tremor which would interfere with recording balance and walking; other factors affecting gait such as musculoskeletal disorders (particularly symptomatic hip, knee and lumbar osteoarthritis), uncorrected vision disturbance, vestibular problems or any other health problem judged to interfere with participation. Major depression, hallucinations or other psychiatric disturbances will be exclusions. Medical problems that might be worsened by donepezil are exclusion criteria and include tachycardia, bradycardia, arrhythmias, and peptic ulcer disease. Finally, use of anticholinergics for parkinsonism, cholinesterase inhibitors for cognitive problems, bladder antispasmodics for urinary urgency or tricyclic antidepressants for depression are contraindications because of their cholinergic actions.

Measures and Outcomes. Falls are a difficult endpoint for clinical trials because the data comes from patient self-reports and in most patients, falls occur infrequently. Falls also depend upon patient activity and falls may be reduced if patients are less active. Finally, falls are generally multi-factorial so that the environment and context, as well as posture, gait and attention play a role in falls. Because of these problems with falls as an index of disturbed mobility, we plan to use two physiological measures associated with falls as surrogate markers for fall risk rather than fall counts. These markers are: 1) increased sway while standing and enhancement of the sway by dual tasking, 2) increased gait variability and augmentation with dual-tasking.

Measurement Device. Balance and gait kinematic performance will be recorded by small, body-worn, inertial sensors, called 'Opals.'¹⁰ The Opals consist of wireless, synchronized, triaxial accelerometers and gyroscopes that record body motion at 120 Hz. The Opals will be applied bilaterally to the ankles and wrists as well as to the sternum and pelvis with Velcro belts.

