of cholinergic markers, does not have alterations in SAI.²¹ SAI is reduced or abolished by an acute dose of the antimuscarinic agent, scopolamine, in normal individuals. In AD subjects who had reductions in SAI, the response to a single dose of a cholinesterase inhibitor, 3 mg of rivastigmine, predicted the response to long-term anticholinesterase inhibitor treatment; those subjects who had an improvement in SAI with the single dose of cholinesterase inhibitor improved with long-term therapy.²² These observations suggest that SAI may identify subjects in our study who have cholinergic deficits as well as be an indicator of the effects of our cholinergic interventions.

Monitoring Activity at Home. Monitoring activity at home will be accomplished with the small inertial sensors that the subject will be asked to wear on their belt and/or a limb.

Clinical Measures. UPDRS, MOCA, , ABC, PDQ-39 total index and mobility domain subscores and falls recorded during the study will be collected.

Data Analysis. A linear mixed model will be used to analyze a crossover with repeated measures design that includes treatment effects, random effects of treatment sequence within subjects and random effects of subjects within treatments. The observations on each subject are repeated measures (week 0 and 6) under different treatment conditions. Since in a typical experiment using repeated measures, two measurements taken at adjacent times are more highly correlated than two measurements taken several time points apart, we will use Bayesian Information Criterion (BIC) to explore optimal covariance structure for the model. The main focus of the study is to determine how the two treatments outcomes change over time, I.E. time by treatment interaction effect. Generalized least square (GLS) and restricted maximum likelihood (REML) will be used to estimate treatment effects and random effects, respectively. In crossover designs, missing data have much greater influence on the analysis than they would in a parallel groups design especially when missing data are not at random such as drop-outs due to the adverse effects of treatments. We will analyze two separate data sets in order to evaluate the impact of missing/non-response. One data set includes all patients who received at least one study drug and another data set only includes the patients who complete the complete treatment sequence.

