1. Adverse effects of donepezil. Donepezil is widely used in PD at the doses proposed in this trial. We anticipate GI effects (anorexia, nausea, diarrhea and vomiting), muscle cramps, insomnia and mild worsening of tremor, which occur commonly but are mild. Serious but rare adverse events include exacerbation of peptic ulcer disease and bradycardia. Drs. [name] and [name] will personally call each patient to discuss any reported side-effects and work with patients on strategies to reduce discomfort.

2. Fall risk during gait and balance testing. Subjects are chosen who can ambulate independently. Testing is conducted with a research coordinator who is trained to be able to assist subjects during testing. If a subject has precarious balance the research assistant will obtain backup assistance and use a safety belt for further safety.

3. Short-latency afferent inhibition is performed with transcranial magnetic stimulation. Subjects with a history of recurrent seizures will be excluded. TMS will occur in the hospital, close to emergency care if necessary. The short-latency afferent inhibition is measured at times that exceed the time for a stimulus at the wrist to reach the sensory cortex. Thus a somatosensory evoked potential will be measured at baseline.

Drs. [name] and [name] will record adverse events and report to the IRB unexpected or serious adverse events. An independent neurologist will review the reported adverse events each six months and make recommendations to the trial leadership as well as the IRB about advisability of continuation of the trial, changing the protocol or other safety concerns. [name], MD, PhD, a member of the OHSU movement disorder section but with no other connection to the clinical trial will serve as the Safety Monitoring Officer.

References

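### The only missing-data check, all treated patients against completers, cannot show whether adverse-effect drop-out has biased the result; a shift (delta) analysis beside it is a cheap improvement

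*Combined protocol and SAP*

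**What the plan says.** The Data Analysis section warns that missing data weigh more heavily in a crossover than in a parallel-group trial, "especially when missing data are not at random such as drop-outs due to the adverse effects of treatments". Its response is this: "We will analyze two separate data sets in order to evaluate the impact of missing/non-response". One set holds everyone given any study drug; "another data set only includes the patients who complete the complete treatment sequence". Both are analysed with the linear mixed model (GLS and REML), with the time-by-treatment interaction as the main focus. No imputation, shift or other not-at-random analysis is planned, and no rule says how to read agreement or disagreement between the sets.

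On timing, the same section says: "The observations on each subject are repeated measures (week 0 and 6) under different treatment conditions". The Protocol section agrees: "At 6 weeks, the subject will return to the clinic for repeat testing with the measures captured at baseline". Between visits, "The subject will be called weekly to ask about side effects or problems with the protocol", and falls are asked about as well. These contacts go on case report forms, but they are not gait or sway measurements.

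**The concern.** The plan names a mechanism and then uses a check that does not test it. A patient with no donepezil week-6 test has no on-drug gait or sway value in either set, so the two fits rest on nearly the same within-patient contrasts. The all-treated likelihood analysis is valid if data are missing at random, which is the condition the plan itself doubts. Dropping the leavers' remaining visits does not test that condition.

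At stake is how agreement would be read. The opening section says that the findings are meant to lead to Phase II B trials. A report that both sets gave the same answer could be taken as reassurance about adverse-effect drop-out, and it would not be.

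**Working it through.** **Inputs.** From the documents: a two-phase crossover, weeks 0 and 6 in each phase, and a mixed model by GLS/REML. There is no sample size, SD, target effect or drop-out rate, so there is no plan figure to reproduce. Assumed, in outcome-SD units (negative = benefit): variances 0.6 (subject), 0.1 (subject by treatment) and 0.3 (residual); true effect -0.20; a share p of 5, 10 or 20% leaving on donepezil. Correlation of leaving with its driver and SD s of individual response: weak (0.2, 0.25), middle (0.4, 0.5), strong (0.7, 0.5).

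**1. Bias if leaving depends on response.** The effect among stayers differs from the effect in all by rho × s × phi(z)/(1-p), where z is the upper-p normal quantile.

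| p | Weak | Middle | Strong |
|---|---|---|---|
| 5% | 0.005 | 0.022 | 0.038 |
| 10% | 0.010 | 0.039 | 0.068 |
| 20% | 0.017 | 0.070 | 0.122 |

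**2. Standard error.** With complete data it is sqrt((4 × 0.3 + s²)/N). For N = 40 this is sqrt(1.2625/40) = 0.178 (s = 0.25) or sqrt(1.45/40) = 0.190 (s = 0.5). With 20% leaving, GLS gives 0.191 and 0.206. Bias over standard error is then 0.017/0.191 = 0.09, 0.070/0.206 = 0.34 and 0.122/0.206 = 0.59; a nominal 95% interval covers 95%, 94% and 91%.

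**3. Does the comparison see it?** Simulation of 900 trials per scenario, N = 40, 20% leaving, REML with random subject and subject-by-treatment effects. The gap is all treated minus completers. The AUC is for the signed gap against unrelated drop-out (0.50 = no discrimination). The Monte Carlo error of a bias is about 0.007.

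| Leaving depends on | Case | Bias, all treated | Bias, completers | Mean gap (SD) | AUC |
|---|---|---|---|---|---|
| nothing | s = 0.25 | +0.007 | +0.007 | 0.000 (0.055) | reference |
| nothing | s = 0.5 | +0.009 | +0.010 | -0.002 (0.055) | reference |
| response | weak | -0.009 | -0.011 | +0.002 (0.057) | 0.50 |
| response | middle | -0.077 | -0.075 | -0.002 (0.054) | 0.50 |
| response | strong | -0.121 | -0.119 | -0.002 (0.058) | 0.50 |
| unseen week-6 value | weak | -0.042 | -0.027 | -0.015 (0.054) | 0.57 |
| unseen week-6 value | middle | -0.098 | -0.075 | -0.023 (0.058) | 0.61 |
| unseen week-6 value | strong | -0.168 | -0.129 | -0.039 (0.056) | 0.68 |
| baseline severity | weak | +0.004 | +0.020 | -0.016 (0.055) | 0.58 |
| baseline severity | strong | -0.007 | +0.073 | -0.080 (0.058) | 0.84 |

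Response-related drop-out leaves no trace in the gap. The largest gap belongs to baseline-related drop-out, where the all-treated result is sound. The gap has the same sign when the all-treated result is biased by 0.168 SD. The largest bias is 0.168/0.206 = 0.82 standard errors (simulated coverage 0.864).

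A large-sample simulation with a different, logistic dependence on response (400,000 subjects per scenario, s = 0.5) gave biases of 0.02 to 0.04 SD at 5% and 0.09 to 0.13 SD at 20%, with gaps of at most 0.001. Covariance structures chosen by BIC were not simulated.

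**4. What a shift analysis would show.** With equal sequence sizes, the estimate moves by (share shifted) × (shift). A benefit of 0.20 SD reaches zero at 0.20/0.05 = 4.0, 0.20/0.10 = 2.0 or 0.20/0.20 = 1.0 SD. At N = 40 that estimate is only about one standard error, so its interval includes zero from the start. For an estimate of 2.5 standard errors, the interval reaches zero at no more than (2.5 - 1.96) × SE/share, about 2.1, 1.1 or 0.6 SD at 5, 10 or 20%. These are upper limits because the imputation standard error grows with the shift (at 20%: 0.207 at no shift, 0.216 at 1 SD).

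**5. Unequal sequences.** Giving the sequences equal weight, the slope is the mean of the two per-sequence shares a and b. It differs from the overall share by ½(a - b)(n2 - n1)/(n1 + n2), which is zero only if the sizes or the shares are equal. With sequences of 22 and 18 and four shifted values, all in the larger, it is ½ × 4/22 = 0.091 against 4/40 = 0.100. The zero point is then 0.20/0.091 = 2.2, not 2.0. GLS allowing for response variance gives 0.091 to 0.093.

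**The case against.** The case for leaving the plan alone is respectable. It recognises the risk, uses a likelihood model on all treated patients, and contradicts nothing. The trial is declared exploratory. The Data Safety Monitoring Plan expects common side effects to be mild and provides follow-up calls, and the Intervention section makes the dose increase conditional on tolerance, so drop-out may be low. Leaving for gastrointestinal effects, cramps or insomnia may have nothing to do with gait response. Every size above is assumed. The comparison is also not wholly blind: it has weak power against drop-out driven by the unseen week-6 value. Finally, the documents do not say that patients who stop drug skip the week-6 test, and home sensor monitoring is planned. All of this stands and keeps the priority modest. The home monitoring, however, has no stated timing or analysis, so it cannot be counted as a substitute.

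A reader might infer more from the tremor passages. The safety plan expects "muscle cramps, insomnia and mild worsening of tremor, which occur commonly but are mild", and the exclusion criteria rule out "significant tremor which would interfere with recording balance and walking". These differ in degree, and interference with a recording concerns patients who are tested. Neither passage says that tremor makes patients leave or that leavers respond worse, so they are not evidence of outcome-related drop-out.

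**Conclusion.** The point holds as a cheap improvement of modest priority. Agreement between the two sets would not show that the result is safe from the drop-out the plan worries about, and a gap would not measure the bias of the all-treated result.

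Under the stated assumptions, bias toward benefit at 20% leaving is about 0.02 to 0.12 SD if response-related and up to about 0.17 SD if related to the unseen week-6 value. It is smaller at lower drop-out and zero if leaving is unrelated. With 40 subjects it stays below one standard error. With 80 the largest case would exceed it (0.168/0.146 = 1.15).

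A reader might conclude that the trial's result will be biased toward donepezil, or that the analysis is invalid. The documents support neither: they do not link leaving to outcome, and they do not settle whether patients who stop drug lack a week-6 test. That the comparison cannot see response-related drop-out follows from the design and held in both simulations; the sizes are illustrations only.

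**What to change.** Keep the all-treated mixed model as the main analysis and label the completer analysis descriptive. Add to the Data Analysis section:

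1. Report drop-out numbers and reasons by treatment and period, from the contacts already on case report forms.
2. For stride time variability (the primary gait measure in Gait Protocol) and the sway measures, if any donepezil week-6 value is missing after donepezil was started, multiply impute missing week-6 values from the mixed model.
3. Shift in the adverse direction only the imputed donepezil week-6 values of patients who left during the donepezil phase. Leave unshifted the imputed values of those who left on placebo or in washout.
4. Extend the shift grid until the refitted estimate reaches zero. Do not end it at the estimate divided by the missing share, which is exact only with equal sequence sizes or equal missing shares in the two sequences.
5. Report the time-by-treatment estimate and interval at each shift and, only if the main interval excludes zero, the shift at which it no longer does. If the estimate does not favour donepezil, report the estimates and intervals only.

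The cost is a few sentences and a little more programming, with no new visits, patients or data. The analysis does not remove bias. Conclusions may become less certain, and the reader must judge which shift is plausible, which the documents cannot settle.

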IRB Document Approval Date: 1/15/2019

NCT Number: NCT02206620

Title: Effects of Cholinergic Augmentation on Measures of Balance and Gait

Principle Investigator: [name]

Effects of Cholinergic Augmentation on Measures of Balance and Gait

Abstract. We will compare the effects of placebo and donepezil, a cholinesterase inhibitor that will enhance the effects of nicotinic and muscarinic cholinergic neurotransmission, on measures of standing postural sway, walking variability, and dual-task cost as indices of fall risk in Parkinson's disease (PD) subjects in a double-blind, placebo controlled, cross-over randomized clinical trial. In addition, short-latency afferent inhibition (SAI), a physiological index of central cholinergic function will be measured to determine if the deficits in balance and gait correlate with abnormalities of the SAI and if SAI is altered by donepezil as a measure of drug efficacy. The attention network test will be administered to determine if changes in gait and balance are mediated by changes in attention.

Hypothesis. Cholinergic systems contribute to mobility in Parkinson's disease (PD). Measures of gait and balance will improve in response to cholinergic augmentation with a cholinesterase inhibitor, donepezil.

Aim 1. Examine the effects of a cholinesterase inhibitor, donepezil, on physiological markers of mobility associated with falls in PD (postural sway in stance and gait variability).

Aim 2. Determine the effects of donepezil on dual-tasking during postural sway and gait variability and on attention using the Attention Network Test.

Aim 3. Correlate Short-latency Afferent Inhibition (SAI), a transcranial magnetic stimulation-induced marker of cortical cholinergic tone, with mobility deficits at baseline and with donepezil treatment.

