forebrain is associated with slower gait⁴ and impairments in working memory, attention and executive function.⁵ In addition, loss of thalamic [¹¹C]PMP, representing loss of PPN cholinergic innervation of the thalamus, is related to falls in PD.⁶ In contrast, the extent of dopaminergic denervation of the striatum evaluated by PET imaging was not correlated with falls.⁶ Finally, neurotoxin lesioning of the cholinergic neurons of the PPN induced gait and postural abnormalities in monkeys.⁷ These observations support the need to examine cholinergic treatments in PD subjects with gait and balance difficulties.

The most direct test of the role of cholinergic systems in postural control to date are two small clinical trials. In a randomized, double-blind, crossover clinical trial of a cholinesterase inhibitor, donepezil, our group found that donepezil reduced falls in PD patients.⁸ An open trial with another cholinesterase inhibitor, galantamine, also reported decreases in falls and freezing of gait (FoG). But these small clinical trials are not conclusive.

Intervention. Cholinesterase inhibitors such as donepezil are standard of care for PD patients with cognitive impairment.⁹ We chose donepezil, an FDA approved drug, because it is possible to create a placebo for the donepezil tablet and it requires only once a day dosing. It is recommended to start donepezil at 5 mg per day to reduce adverse effects (FDA approved drug insert). We will increase the dose to 10 mg/day after 3 weeks, if tolerated, because that is the schedule used in our pilot study and this titration was well tolerated.⁸ Donepezil has a half-life of 70 hours and it requires approximately 15 days to reach steady state. The maximum effects on cognitive measures occur within 3 weeks and loss of effect requires more than 3 weeks and less than 6 weeks (FDA approved drug insert). In our pilot study there were more falls at 3 weeks and 5 mg/day of donepezil than at 6 weeks and 10 mg/day of donepezil and 10 mg was more effective than 5 mg on cognitive measures in PD.⁹ Washout between phases will be 6 weeks to minimize carry-over of effects.

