We examined gait variability during a 2-minute walk in 20 PD subjects and 20 age-matched control subjects as part of an ongoing trial. The coefficient of variation of stride duration and cadence were significantly larger in the PD group. Figure 3 illustrates the variability in stride duration for each stride during a 2-minute walk for a representative subject with PD and an age-matched control subject. The PD subject's stride time was longer (1.04 vs 0.98 sec), representing slower gait and more variable with a larger coefficient of variation (3.26 vs 1.59) than the control subject.

Gait Protocol. Gait control measurements will rely upon the ankle gyroscopes for spatial and temporal gait measures with stride time variability the primary gait outcome. Subjects will walk

at their natural pace down a 20-meter long hallway, turn around at the end and return to the starting point and then continue walking back and forth for two minutes. The 180-degree turns during the walking are automatically detected and analyzed separately by Mobility Lab.

Dual Tasking Unmasks Instability. There is abundant evidence that gait and balance are under cortical control, requiring attention, as demonstrated in studies of gait and balance with concurrent mental tasks (dual-tasking).¹⁷ Dual tasking increases measures of gait instability in patients with PD.¹⁸ These observations indicate that cholinergic drug effects could be mediated by altering the ability to dual task and thereby influencing the risk of falling.

Dual Task Paradigm. The effects of dual tasking on sway and gait variability will be assessed with a mental task of counting backwards by 3s from various starting numbers. While performing the mental task, subjects will wear a small microphone connected to a small, custom-made computer with voice recording to record their performance on the mental task. Responses will be recorded for accuracy. Subjects will perform the counting backwards by 3s as a single task while sitting and then during standing and walking. This will allow calculating the dual-task costs on balance and walking.¹⁸

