Interpretation. We are especially interested in determining whether gait and balance are directly influenced by cholinergic manipulation or whether changes in attention capacity are primarily responsible for changes in balance and gait. If, for example, we find that ability to balance and walk during dual tasking is altered out of proportion to changes during standing and walking without dual tasking, it would suggest that cholinergic systems mainly contribute to attentional capacity required for balance and gait. Because of the evidence linking executive dysfunction with gait disorders, we expect that the executive attention which has been related to falls and to gait may be affected out of proportion to alerting and orienting aspects of attention although Posner and colleagues have linked alerting to cholinergic function.

Privacy, Confidentiality and Data Security. Standard institutional practices will be followed as described in the OHSU Information Security and Research Data Resource Guide (http://ozone.ohsu.edu/cc/sec/isg/res_sec.pdf) to maintain the confidentiality and security of data collected in this study. Study staff is, and will continue to be, trained with regard to these procedures. Paper files will be stored in locked filing cabinets in restricted access offices at OHSU. Electronic data is stored on restricted drives on the OHSU network and on encrypted

computers. Access to data/specimens is restricted to study personnel and requires OHSU ID/password authentication.

Upon enrollment, subjects will be assigned a code that will be used instead of their name, medical record number or other personally identifying information. Electronic files for data analysis will contain only the subject code.

Codes will not contain any part of the 18 HIPAA identifiers (initials, DOB, MRN, etc.)

The key associating the codes and the subjects personally identifying information will be restricted to the PI and study staff. The key will be kept secure on a restricted OHSU network drive in a limited access folder.

Data will be transferred to/from The Michael J. Fox Foundation in files using encryption. The data released to the Michael J. Fox Foundation will include only de-identified (coded) data.

Data Safety Monitoring Plan (DSMP). There are three safety issues.

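### The dual-task example in the Interpretation section leaves out counting performance, so a shift of effort between tasks could be read as a change in attentional capacity

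*Combined protocol and SAP*

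**What the plan says.** The Interpretation section states a particular interest in whether cholinergic manipulation affects gait and balance directly or by way of attention. As an example it takes the case where "ability to balance and walk during dual tasking is altered out of proportion to changes during standing and walking without dual tasking"; in that case "it would suggest that cholinergic systems mainly contribute to attentional capacity required for balance and gait".

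The Dual Task Paradigm section describes the mental task: "Subjects will perform the counting backwards by 3s as a single task while sitting and then during standing and walking". A microphone and voice recorder capture how subjects perform it, and "Responses will be recorded for accuracy". The stated use follows: "This will allow calculating the dual-task costs on balance and walking". The section cites a review of dual-task walking at this point, but does not say that a cost on counting is taken from it. It states no pacing of the counting and no instruction on which task to favour.

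Aim 2 is to "Determine the effects of donepezil on dual-tasking during postural sway and gait variability and on attention using the Attention Network Test". The Data Analysis section describes a mixed model for the crossover and does not list outcomes one by one. Neither names a counting outcome.

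The Abstract includes the Attention Network Test to find out whether gait and balance changes work through attention. The section on that test describes it as one reaction-time task.

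The Intervention section gives reason to expect cognitive effects of donepezil: "The maximum effects on cognitive measures occur within 3 weeks", and, from a cited study, "10 mg was more effective than 5 mg on cognitive measures in PD". Testing is at 6 weeks.

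**The concern.** A dual task has two outputs, and a subject can trade one for the other. Someone who counts less while walking may walk more steadily with no gain in capacity. Someone with more capacity may walk more steadily while counting just as well. A comparison that looks only at the motor output cannot tell these apart.

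The comparison between treatments is safe if counting is the same under both. The documents do not secure that: no pacing or task priority is stated, and the protocol's own rationale is that donepezil acts on cognition. Accuracy is the only counting measure named. If it is scored as the share of answers that are right, it will not register slower counting at the same error rate.

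What is at stake is the attribution to attention, which the Interpretation section singles out and which the study intends to carry into more focused questions and later trials. Dual-task sway and gait variability as indices of fall risk are not affected.

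**Working it through.** The plan gives no figure on this point, so there is none to reproduce. The check has two parts.

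**1. Which measures enter the inference.** The Interpretation example compares dual-task gait and balance with single-task gait and balance. The Dual Task Paradigm section names costs on balance and walking. Aim 2 names sway, gait variability and the Attention Network Test. Counting is collected, with a sitting reference, but none of these places gives it a cost, an outcome or a role in the reading. The silence of the Data Analysis section adds little, because that section names no individual outcome. The gap is therefore in analysis and interpretation, not in data collection.

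**2. Whether the omission can change the reading.** The only input from the documents is a stride-duration coefficient of variation (CV) of 3.26, from one representative subject with PD (described before the Gait Protocol section). It serves as the single-task value. Everything else is assumed.

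- Motor cost = dual-task CV / single-task CV − 1
- Counting cost = 1 − dual-task correct per minute / sitting correct per minute

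| | Placebo | Donepezil, case A | Donepezil, case B |
|---|---|---|---|
| Single-task CV | 3.26 | 3.26 | 3.26 |
| Dual-task CV | 4.89 | 4.40 | 4.40 |
| Motor cost | 4.89/3.26 − 1 = 50% | 4.40/3.26 − 1 = 35% | 35% |
| Sitting, correct per minute | 36 | 36 | 36 |
| Dual-task, correct per minute | 27 | 21.6 | 27 |
| Counting cost | 1 − 27/36 = 25% | 1 − 21.6/36 = 40% | 25% |
| Accuracy | 90% | 90% | 90% |

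In both donepezil cases dual-task CV falls by (4.89 − 4.40)/4.89 = 10% against 0% in the single task, so the condition in the example is met. In case A the 15-point gain in motor cost is matched by a 15-point loss in counting cost, which fits a shift of effort. In case B counting holds, which supports the capacity reading. The example gives the same answer for both.

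Holding accuracy at 90% is itself an assumption (27 of 30, 21.6 of 24 and 36 of 40 responses per minute). A second set of values lets accuracy move. Single-task CV is again 3.26; dual-task CV is 4.24 on placebo (cost 30%) and 3.75 on donepezil (cost 15%). Sitting accuracy is 90% on both; dual-task accuracy is 81% on placebo (1 − 81/90 = 10% cost) and 67.5% on donepezil (1 − 67.5/90 = 25% cost). Here the planned accuracy record would reveal the trade-off, provided someone compares it by treatment. The plan does not say that anyone will.

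**The case against.** The strongest reply is that attention is not judged from gait and balance alone. The Attention Network Test is in the trial to address mediation, and the Interpretation section goes on to the attention networks. The dual-task reading is offered only as an example, in tentative words, in a study that calls itself exploratory. All of this stands, and a reader who infers that the whole attention inference ignores cognition goes too far. But a single reaction-time task done on its own does not show how effort was split between counting and walking or standing, and no rule links its result to the dual-task comparison.

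A second reply is that the documents do not suggest subjects will count less on donepezil. The Intervention section reports cognitive benefit, which points to better counting. The dose comparison comes from a study that, by its title in the reference list, was in PD dementia, whereas this trial requires a MOCA of 23 or above. This also stands: case A is a possibility, not a prediction. It does not remove the point, because the plan states no comparison of counting by treatment that would show which case occurred.

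A reader might also infer that the plan errs by missing a gain that goes wholly into counting. It does not, for the question asked: if balance and gait are unchanged, there is no change in them to attribute.

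Finally, a sitting counting condition has its natural use as a reference for counting, so the team may well intend to use it. Nothing rules this out, but it is not written down.

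**Conclusion.** The point holds in a limited form. The dual-task example omits counting, which the trial records, and so cannot separate a gain in capacity from a shift of effort if counting differs between treatments. In the illustration, the same 15-point fall in motor cost accompanies a counting cost that either rises 15 points or does not move. Apart from the 3.26, those values are assumed. They show that the reading can go wrong, not that it will.

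A reader might want an error rate for false capacity findings. The documents state no sample size, variance or significance rule for this inference, so any such rate would describe the assumptions rather than the plan. Nor do the documents support a test on the sum of motor and counting costs. Such a sum is neutral to a trade-off only on the scale on which the two sides are equal. If, for instance, a 15-point change were 0.5 SD for motor cost and, with counting twice as variable, 0.25 SD for counting, the standardised sum would be 0.5 − 0.25 = 0.25 SD rather than zero.

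This is an improvement to consider, not a flaw in the design.

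**What to change.** Add a short paragraph to the analysis plan:

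- From the planned voice recordings, score counting as correct responses per minute as well as accuracy, while sitting and in each dual-task condition.
- Compute the counting dual-task cost (dual-task against sitting), analyse it by treatment in the same mixed model, and report it with its confidence interval beside the motor costs.
- Draw the attentional-capacity reading from the dual-task result only when motor cost improves and the counting-cost estimate and interval do not indicate worsening. A non-significant decline is not by itself evidence of no decline.
- If counting worsens, report a possible trade-off and draw no capacity conclusion from that comparison.
- Keep the motor costs as planned, and read the Attention Network Test beside this result.

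The cost is some extra scoring and analysis, with no new visits or tests. The downside is that, with a small sample, the counting interval may be too wide to exclude a trade-off, so the dual-task reading may be inconclusive more often.
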